#### **F4. Change Trajectory**

We will use latent growth curve modeling to explore the trajectory of change in our outcome measures specified above. These models will initially be specified as parallel growth processes (i.e. simultaneous modeling of suicide attempts, suicidal ideation, and psychiatric hospitalization) to account for shared variance, but will be tested individually if a parallel growth model cannot be fit. Using data collected across our 5 assessments, we will estimate intercept (i.e. mean) and slope (i.e. linear rate of increase/decrease) for each of these latent suicide risk constructs. As we expect participants will show clinical improvements at the end of the CLASP protocol, with some participants deteriorating in the follow-up (with a similar, but more pronounced intensity of response for SAFE participants) we will also investigate quadratic slope (i.e. curvilinear change trajectory). To account for time, we will fix our initial two time points, and allow MPlus to estimate the remaining time parameters. We first fit unconditional models to identify the optimal change trajectory for each outcome.

Once the optimal growth trajectory has been identified, we then fit conditional growth models in which growth parameters (i.e. intercept, slope, quadratic slope) are regressed on selected predictor variables (i.e. treatment assignment, covariates, and/or moderator variables of interest). We chose this analytic approach because it permits us to both take advantage of the repeated suicide assessments and to model variations associated with the implementation and cessation of treatment. We will be able to add additional predictors to the model iteratively, to explore the unique and overlapping predictive utility of each measure. However, we recognize that as with any latent variable modeling approach, we may experience difficulty with model fit. In the event that we are unable to fit a model to the data, we will either modify our model (i.e. exclusion of a risk variable, inclusion of covariance between predictors, change in time parameterization, etc.) or employ a simplified multilevel modeling approach (i.e. HLM) or multiple linear regressions.

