Valued Living Questionnaire [59]	X	X
Psychiatric Symptoms		
Brief Symptom Inventory [60]	X	X
Overall Functioning		
WHODAS II [61]	X	X
Treatment Utilization		
Treatment History Interview [62]	X	X

At 3, 6, 9, and 12 month follow-up, the assessments will be administered by an evaluator blind to patient study condition. Note that all evaluators will be blind to study condition at baseline, as that assessment occurs before individuals are assigned to treatment groups. In order to maintain the integrity of the treatment blind: 1) blind evaluations will be conducted by personnel not otherwise affiliated with this study and whose office space is physically separate from the clinical offices of this project, 2) patients will be instructed at each visit that they are not to make any mention of their treatment condition while they are being interviewed by their assigned rater; and 3) at the beginning of each rating session, the rater will remind the patient that she/he is not to mention treatment condition during the interview with the rater.

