#### **F5. Statistical Power**

Statistical power was based upon effect size estimates derived from the CLASP pilot as well as our judgment about how large a difference would represent a clinically significant difference. In our pilot study, for suicide attempts, we found that 3 of 39 (~8%) individuals assigned to CLASP made a suicide attempt compared to 10 of 47 (~21%) randomized to control, yielding an effect size between small and medium ( $d = .38$ ; 95% CI: .31 - .45). Similarly, for psychiatric re-hospitalization, we found that 8 of 39 (~20.5%) individuals assigned to CLASP were re-hospitalized for suicide risk compared to 17 of 47 (~36%) randomized to control, yielding an effect size between small and medium ( $d = .35$ ; 95% CI: .28 - .41). Consequently, we believed that it was important to power the proposed study for effect sizes slightly larger than small ( $\sim d = .25$ ) to provide adequate coverage for the full range of expected effect sizes.

Sample size for effect size and odds ratio comparisons for the primary treatment outcomes was estimated using Fisher's Exact Test using our primary treatment outcome, # of suicide attempts. Assuming the proportions identified in the CLASP pilot,  $\alpha = .05$ , a one-tailed hypothesis test, and our projected sample of 200, our power estimate for this conservative test will be .82. It should also be noted that given the longer follow-up period in the current study, we hypothesize that the difference in

proportions obtained in our pilot study are likely to be higher due to the longer period of risk assessed. Consequently, the proposed study design should have ample power to test our primary hypothesis.

To estimate power for latent growth curve models, we used Zhang & Wang's [81] simulation procedure for SAS 9.1.3. Our simulation assumed five repeated measures assessments (Baseline, 3-, 6-, 9-, and 12-month), a moderate correlation between slopes and intercepts ( $r = .30$ ), a total missing data rate of ~30%, and 2500 simulation replications per sample size. We simulated sample sizes ranging from 50 to 300 in 10 participant intervals for our lower-bound effect size estimate ( $d = .28$ ). The proposed sample of participants ( $N = 200$ ) should be adequate (Power > .80) to detect even our lower-bound effect size for the full sample.

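### The growth model lets treatment affect the intercept although baseline precedes randomisation; for outcomes with a baseline value, fixing that effect at zero would gain some precision on the slopes

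*Combined protocol and SAP*

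**What the plan says.** F4 first fits unconditional growth curves to each outcome. It then fits conditional models in which "growth parameters (i.e. intercept, slope, quadratic slope) are regressed on selected predictor variables (i.e. treatment assignment" is the operative phrase, with covariates and moderators as further possible predictors. All three growth parameters may therefore depend on treatment.

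Three other statements bear on what the intercept means:

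- **Timing of baseline.** D5 explains that evaluators are blind at baseline, "as that assessment occurs before individuals are assigned to treatment groups".
- **Waves.** F5 bases the growth-model power on "five repeated measures assessments (Baseline, 3-, 6-, 9-, and 12-month"), so baseline is the first of the modelled waves.
- **Time coding.** F4 says "Using data collected across our 5 assessments, we will estimate intercept (i.e. mean) and slope", and later "we will fix our initial two time points, and allow MPlus to estimate the remaining time parameters". It gives no values for the two fixed scores.

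F4 presents this modelling as a way to explore trajectories. The primary analysis is in F3.2: an odds ratio for the proportion of patients with an attempt.

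**The concern.** Two arms formed by randomisation after baseline have the same expected baseline mean. If the intercept is the baseline level, a treatment effect on it is a parameter whose true value is already known to be zero. Estimating it lets chance baseline differences feed into the estimated slope difference, much as leaving out a baseline adjustment would. It also adds, for each outcome, a treatment test that is null by design in a correctly specified model, while F1 adjusts interpretation for the number of tests.

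At stake is the precision of the treatment-by-time estimates for the repeated scales. F1 gives maximising power as a reason for choosing growth models, so this free parameter works against the plan's own aim.

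**Working it through.** **1. The plan's own figure.** F5 reports power above .80 for the growth model at N = 200 and d = .28. It cannot be rebuilt: F5 omits the variance components, the scale of d, and the alpha and sidedness for this model. The check below is therefore of relative precision only.

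**2. Inputs.** From F5: five waves, intercept-slope correlation r = .30, and "a total missing data rate of ~30" per cent. From D2: 100 of 200 patients in CLASP, hence 100 per arm. Assumed: time scores 0 to 4 with the intercept at baseline; a continuous outcome; intercept variance 1; slope variance τ of .01, .02, .05 or .1 per wave; residual variance σ² of .5, 1 or 2; monotone dropout with 100, 92.5, 85, 77.5 and 70% retained at the five waves.

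**3. Formula with complete data.** For times 0 to 4, n = 5, Σt = 10 and Σt² = 30, so the determinant is 150 − 100 = 50. Per-person least-squares intercepts and slopes then have

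- W11 = 1 + 0.6σ²
- W12 = r√τ − 0.2σ²
- W22 = τ + 0.1σ²

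The slope-effect variance is 2·W22/100 with a free intercept effect. Fixing that effect at zero reduces it by the fraction W12²/(W11·W22).

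- τ = .05, σ² = 1: W12 = .067 − .200 = −.133; reduction .0177/(1.6 × .15) = 7.4%.
- τ = .01, σ² = 2: W12 = .03 − .40 = −.37; reduction .1369/(2.2 × .21) = 29.6%.
- τ = .1, σ² = .5: W12 = .095 − .100 = −.005; reduction about 0%.

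The last case shows why the gain can vanish: a positive true correlation offsets the negative sampling correlation between intercept and slope.

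**4. With dropout.** The same comparison uses the expected information matrix summed over dropout patterns. Each cell gives the percentage cut in variance for the linear model / for the linear term when a quadratic mean is added (random intercept and slope only).

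| τ | σ² = .5 | σ² = 1 | σ² = 2 |
|---|---|---|---|
| .01 | 6 / 13 | 15 / 22 | 27 / 31 |
| .02 | 4 / 12 | 12 / 21 | 25 / 30 |
| .05 | 1 / 10 | 8 / 19 | 19 / 29 |
| .1 | 0 / 8 | 4 / 17 | 14 / 27 |

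The linear model gives 0 to 27%, median about 10%, with 2 of 12 cells at 20% or more. The linear term of the quadratic model gives 8 to 31%, median about 20%.

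Reading the missing-data rate as 30% of all cells, on a different grid (baseline reliability .3 to .7), gives 0.1 to 24% and 8 to 29%. On that grid the 12-month difference from the quadratic model gains less, 0.3 to 12%.

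**5. In power terms.** Assume unconstrained power of exactly 80%, two-sided .05. Power becomes Φ(2.80/√(1 − cut) − 1.96). A 10% cut gives 84%; a 27% cut gives 91%.

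**6. If the curve shape is wrong.** Suppose the true effect is 0 at baseline and 1 unit at every follow-up, and a straight line is fitted. Over the same grid the unconstrained fit returns an intercept effect of about 0.35 to 0.36 and a slope effect of 0.22 to 0.23. The constrained slope effect is 0.23 to 0.28, which is 2 to 30% larger.

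**The case against.** The strongest reply has four parts.

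- **The baseline intercept is inferred.** F4 glosses the intercept only as a mean, gives no time scores and allows the time parameterisation to change. If time were centred elsewhere, the intercept would be a legitimate treatment contrast and the constraint would be wrong. This stands, and it is why the time scores must be stated with the constraint. Fixing the first two scores and freeing the rest is nevertheless the usual coding that puts the intercept at baseline.
- **Few of F4's named outcomes qualify.** Its parallel model covers attempts, ideation and hospitalisation. Attempts and re-hospitalisations are counted after enrolment (F3.1), and the D5 table marks LIFE at follow-up only. This stands. What remains is C-SSRS ideation intensity, BSI, WHODAS and SS-B, all marked at baseline and follow-up.
- **The gain may be negligible.** At r = .30 the linear-model cut starts near zero. This stands for the linear model. It does not hold for the linear term of the quadratic model that F4 says it will investigate, where no cell falls below about 8%.
- **The unconstrained model is valid and exploratory.** Also true: this is a matter of efficiency, not an error that biases the trial.

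A reader might infer that any reported intercept effect must be a false positive and that the constraint costs nothing. Neither follows. Randomisation equalises the baseline mean, not an intercept implied by a fitted curve, and step 6 of the working shows misfit producing a non-zero intercept effect and shifting the constrained slope. A reader might also claim larger gains by assuming a negative intercept-slope correlation, but F5 assumes a positive one.

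**Conclusion.** The point holds as an efficiency improvement to a secondary-tier, exploratory analysis. As written, F4 spends a parameter on a treatment effect that is zero by design if the intercept is at baseline. The price is a slope-effect variance higher than necessary by an amount the documents do not determine: near nothing to about a quarter in the linear model, and somewhat more for the linear term of the quadratic model.

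These sizes rest on the assumed variance components, a continuous outcome, monotone dropout and a correctly specified curve. It would go too far to infer that the trial is underpowered or that its efficacy conclusion is compromised: F3.2 carries the efficacy analyses, and the primary test does not use this model.

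**What to change.** In F4:

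1. State the time scores, with the intercept at baseline.
2. For C-SSRS ideation intensity, BSI, WHODAS and SS-B, set the treatment effect on the intercept to zero and regress only the linear and quadratic slope terms on treatment.
3. Include the urn stratification variables of D6 (gender, number of previous attempts, admission for ideation or attempt) as predictors of the intercept. F4 already allows covariates, so this changes no method.
4. Do not apply the constraint to LIFE ideation, attempts or re-hospitalisations; specify their models separately.
5. Report the unconstrained fit as a sensitivity check, and compare the fitted intercepts with the observed baseline means.

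The cost is one model constraint and one additional fit per outcome, with no new data. The small downside is the possible shift in the slope estimate under a misspecified curve, which item 5 is there to reveal. The change should be written before analysis, because F4 leaves room to modify the model when fit is poor.

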#### **F5. Statistical Power**

Statistical power was based upon effect size estimates derived from the CLASP pilot as well as our judgment about how large a difference would represent a clinically significant difference. In our pilot study, for suicide attempts, we found that 3 of 39 (~8%) individuals assigned to CLASP made a suicide attempt compared to 10 of 47 (~21%) randomized to control, yielding an effect size between small and medium ( $d = .38$ ; 95% CI: .31 - .45). Similarly, for psychiatric re-hospitalization, we found that 8 of 39 (~20.5%) individuals assigned to CLASP were re-hospitalized for suicide risk compared to 17 of 47 (~36%) randomized to control, yielding an effect size between small and medium ( $d = .35$ ; 95% CI: .28 - .41). Consequently, we believed that it was important to power the proposed study for effect sizes slightly larger than small ( $\sim d = .25$ ) to provide adequate coverage for the full range of expected effect sizes.

Sample size for effect size and odds ratio comparisons for the primary treatment outcomes was estimated using Fisher's Exact Test using our primary treatment outcome, # of suicide attempts. Assuming the proportions identified in the CLASP pilot,  $\alpha = .05$ , a one-tailed hypothesis test, and our projected sample of 200, our power estimate for this conservative test will be .82. It should also be noted that given the longer follow-up period in the current study, we hypothesize that the difference in

proportions obtained in our pilot study are likely to be higher due to the longer period of risk assessed. Consequently, the proposed study design should have ample power to test our primary hypothesis.

To estimate power for latent growth curve models, we used Zhang & Wang's [81] simulation procedure for SAS 9.1.3. Our simulation assumed five repeated measures assessments (Baseline, 3-, 6-, 9-, and 12-month), a moderate correlation between slopes and intercepts ( $r = .30$ ), a total missing data rate of ~30%, and 2500 simulation replications per sample size. We simulated sample sizes ranging from 50 to 300 in 10 participant intervals for our lower-bound effect size estimate ( $d = .28$ ). The proposed sample of participants ( $N = 200$ ) should be adequate (Power > .80) to detect even our lower-bound effect size for the full sample.

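### F5 aims to power the study for d of about .25, but its only power figure for the primary outcome (.82) is at the pilot difference (d = .38); at d = .25, 200 patients give about .48 to .54

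*Combined protocol and SAP*

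**What the plan says.** F5 (Statistical Power) starts from two pilot effects: d = .38 (interval .31 to .45) for suicide attempts, 3/39 against 10/47, and d = .35 (.28 to .41) for re-hospitalization, 8/39 against 17/47. It then says that "it was important to power the proposed study for effect sizes slightly larger than small", given as about d = .25, "to provide adequate coverage for the full range of expected effect sizes".

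The next paragraph turns to the primary outcome: "Sample size for effect size and odds ratio comparisons for the primary treatment outcomes was estimated using" Fisher's exact test. The condition is stated openly: "Assuming the proportions identified in the CLASP pilot", with alpha .05, "a one-tailed hypothesis test, and our projected sample of 200, our power estimate for this conservative test will be .82". F5 adds that "given the longer follow-up period in the current study, we hypothesize that the difference in" proportions will be larger than in the pilot, and concludes that "the proposed study design should have ample power to test our primary hypothesis".

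The last paragraph reports a simulation for latent growth curve models at d = .28 and says that 200 participants "should be adequate (Power > .80) to detect even our lower-bound effect size for the full sample".

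Elsewhere, F3.2 names the proportion of patients with an attempt as the primary dependent measure, estimated by a covariate-adjusted odds ratio with a robust confidence interval. F1 favours growth modelling wherever possible, and F4 includes suicide attempts in those models.

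**The concern.** F5 sets its aim at d of about .25, then calculates power for the primary outcome at an effect half as large again (.38/.25 = 1.52). No power at .25 is given for any outcome. The aim, the .82 and the claim of ample power follow one another, and nothing says that the aim is not carried through to the primary comparison.

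F5 is where a reader learns which effects the primary comparison can detect. If the result is null, whether the trial could have seen a benefit of d = .25 (about 9 percentage points in attempts) decides how that null is read. On F5's wording the reader would suppose that it could.

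**Working it through.** **Inputs.** Pilot rates from F5: CLASP 3/39 = .0769, SAFE 10/47 = .2128. One-tailed alpha .05 and N = 200 from F5. Allocation of 100 per arm, inferred from the 100 significant others planned for the CLASP arm (D2).

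**Method.** Enumerate every 2×2 table for 100 against 100, weight each by the two binomial probabilities, and sum the weights of the tables that reject. Two tests:
- Fisher, the planning calculation of F5: reject if the one-tailed hypergeometric p is at most .05.
- Unadjusted odds ratio: reject if log(OR)/SE < −1.645, where SE = √(1/a + 1/b + 1/c + 1/d) over the four cells, with 0.5 added to each cell when one is zero. With a single binary predictor the robust and model-based variances coincide, so this is the unadjusted form of the F3.2 estimate.

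**Step 1: reproduce the .82.** At .0769 against .2128, Fisher power is .833. A continuity-corrected normal approximation gives .816. The stated figure stands. The odds-ratio test gives .875.

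**Step 2: identify the scale of d.** F5 does not define d, but its values show which scale fits. Cohen's h, 2·arcsin√p_SAFE − 2·arcsin√p_CLASP, is .397 for attempts (.379 with the rounded 8% and 21%) and .350 for re-hospitalization. The pooled-SD difference gives .382 and .353. Both fit F5's .38 and .35. A logit-based d would be .62 to .65 for attempts and does not fit.

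**Step 3: convert d to a CLASP rate.** With h, p_CLASP = sin²(arcsin√.2128 − d/2). At d = .25: sin²(.4794 − .125) = sin²(.3544) = .120, a difference of .213 − .120 = 9.2 points after rounding from unrounded rates.

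**Step 4: power, 100 per arm, control rate 10/47.**

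| Effect | CLASP rate | Fisher | Unadjusted odds ratio |
|---|---|---|---|
| d = .25 (F5's aim) | 12.0% | .475 | .544 |
| d = .28 (growth-model value) | 11.1% | .559 | .627 |
| d = .31 (F5's lower limit, attempts) | 10.2% | .640 | .704 |
| d = .35 | 9.0% | .738 | .794 |
| d = .38 | 8.1% | .802 | .849 |
| Pilot rates | 7.7% | .833 | .875 |

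Root-finding puts the smallest d with .80 power at .379 (Fisher) and .353 (odds ratio), differences of 13.1 and 12.4 points.

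**Step 5: how far this depends on the assumptions.** On the pooled-SD scale, power at d = .25 is .476 and .545. Control rates from 21% to 40% give .475 to .490 (Fisher) and .543 to .549 (odds ratio). A higher 12-month event rate therefore does not by itself rescue d = .25. For scale only, .80 at d = .25 would take about 220 per arm by Fisher or 200 by the odds-ratio test.

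**Step 6: the 12-month argument.** The documents give no figure, so take as an assumption that cumulative hazard rises by 25% in both arms: 1 − (1 − .0769)^1.25 = .095 and 1 − (1 − .2128)^1.25 = .258. Fisher power is then about .90; with a 50% rise it is about .94. This is power at a difference larger than the pilot's. It is not power at d = .25.

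**The case against.** **The .82 is correct and its condition is disclosed.** This stands. The sentence that gives .82 also gives the pilot proportions, the alpha, the single tail and the sample size. A reader might infer that F5 miscalculated, or concealed what the .82 rests on; the text supports neither. F5 also never claims .80 power at d = .25 for attempts.

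**The .25 aim is study-wide and lies below what F5 expects for attempts.** Partly stands. The aim follows estimates for two outcomes, and F5's interval for attempts starts at .31. So a reader should not infer that power is about one half across the expected range. But the primary outcome belongs to the study, and at .31 power is .64 or .70, still short of .80. Re-hospitalization does no better at d = .25 (control rate 17/47): .491 and .549.

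**The growth models cover small effects.** It is tempting to dismiss these as exploratory because F4 says that it explores trajectories. The documents do not support so simple a dismissal: F1 favours growth models wherever possible as tests of the aims, and F4 puts attempts in them and regresses growth on treatment assignment. Even so, F5's figure is for d = .28 in those models, while F3.2 names the proportion with an attempt as the primary measure. It does not establish power at .25 for that comparison.

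**The .54 is not the power of the planned analysis.** This stands. F3.2 adjusts for covariates and adds an ordinal GEE analysis. Neither can be computed, because the covariates and the ordinal categories are not given. The .54 is an approximation, and F5 offers no figure for either analysis.

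**Longer follow-up should enlarge the difference.** It may, and power could then exceed .82 (step 6). F5 words this as a hypothesis and puts no number on it, and it leaves power at d = .25 where it was.

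**Conclusion.** The point holds as an unmet aim beside an unqualified conclusion. F5 says that the study should be powered for d of about .25; for the primary comparison, 200 patients give about .48 by the Fisher planning calculation and about .54 for an unadjusted odds ratio. Ample power is a fair description only for effects about as large as the pilot difference.

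The conclusion rests on equal allocation, F5's one-tailed alpha, complete outcome data, a control rate near the pilot's (the answer barely moves up to 40%), and a scale for d inferred from F5's own two values. The adjusted analysis could differ somewhat from the unadjusted proxy.

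A reader might go further and conclude that the sample size must rise. The documents do not require that: N = 200 is consistent with the pilot-sized effect on which the calculation is openly based. What needs correcting is what F5 says N = 200 can detect.

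**What to change.** Keep N = 200 and the analysis, and revise F5 in two places.

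1. Withdraw the aim of covering d of about .25 for the primary outcome. Alternatively, state the power there (about .48 by the Fisher planning calculation; about .54 for an unadjusted odds ratio, labelled an approximation) and at d = .31 (.64 and .70).
2. Limit the ample-power statement to effects about as large as the pilot difference, and label the 12-month gain an unquantified assumption.

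The cost is a few sentences, with no extra patients and no change to the analysis. The stated power for the primary outcome will read less favourably.
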